12.0 Descriptive Factors

- 12.1 Prior ET/PV disease specific therapy (including drugs, or splenectomy): Yes vs no.
- 12.2 Prior bleeding events felt to be related to underlying disease: Yes vs no.
- 12.3 Prior thrombosis: Yes vs no.
- 12.4 Type of Myelofibrosis at registration: Primary Myelofibrosis (PMF) vs. Post ET Myelofibrosis vs. Post PV Myelofibrosis.
- 12.5 MF DIPSS Risk at time of registration (Appendix VI): Low vs. Int-1 vs. Int-2 vs. high

13.0 Treatment/Follow-up Decision at Evaluation of Patient

- 13.1 Patients who are without progression will continue treatment per protocol.
- 13.2 Patients who develop PD while receiving therapy will go to the event-monitoring phase.
- 13.3 Patients who go off protocol treatment for reasons other than PD will go to the event-monitoring phase per Section 18.0.
- 13.4 A patient is deemed *ineligible* if after registration, it is determined that at the time of registration, the patient did not satisfy each and every eligibility criteria for study entry. The patient will go directly to the event-monitoring phase of the study (or off study, if applicable).
 - If the patient received treatment, all data up until the point of confirmation of ineligibility must be submitted. Event monitoring will be required per Section 18.0 of the protocol.
 - If the patient never received treatment, on-study material and the end of active treatment/cancel notification form must be submitted. No further data submission is necessary.
- 13.5 A patient is deemed a *major violation*, if protocol requirements regarding treatment in cycle 1 of the initial therapy are severely violated that evaluability for primary end point is questionable. All data up until the point of confirmation of a major violation must be submitted. The patient will go directly to the event-monitoring phase of the study. Event monitoring will be required per Section 18.0 of the protocol.
- 13.6 A patient is deemed a *cancel* if he/she is removed from the study for any reason before any study treatment is given. On-study material and the End of Active Treatment/Cancel Notification Form must be submitted. No further data submission is necessary.

14.0 Body Fluid Biospecimens

14.1 Summary Table of Research Blood and Body Fluid Specimens to be Collected for this Protocol

Correlative Study (Section for more information)	Mandatory or Optional	Blood or Body Fluid being Collected	Type of Collection Tube (color of tube top)	Volume to collect per tube (# of tubes to be collected)	Prior to Treatment on C1D1, C2D1, C3D1	Process at site? (Yes or No)	Temperature Conditions for Storage /Shipping
Banking	Mandatory	Serum	Red	10 mL (1)	X	yes	Freeze

14.2 Blood/Blood Products Handling

14.21 All samples must be collected **Monday-Friday ONLY.**

14.22 Label specimen tube(s) with protocol number, patient study ID number, and time and date blood drawn.

14.23 Collect and processing

14.231 Serum specimens will be collected per schedule as outlined in Section 14.1. Collect 10 mLs of No Additive blood and allow the blood to clot at room temperature x 30 minutes. Centrifuge the blood at 3000 rpm x 10 minutes. Carefully aliquot the 1.0 mL of serum into three aliquots and 0.5 mL into the 4th aliquot and freeze at - 80°C freezer until requested.

15.0 Drug Information

15.1 P1101 (PEG-P-IFNa-2b)

15.11 Background:

P1101 is a long-acting interferon that has only one major form as opposed to the 8-14 isomers of other FDA approved pegylated interferon products that are indicated for the treatment of hepatitis B and C. With P1101, it is anticipated that a reduced dosing frequency will be possible (once every two or more weeks) compared to that required with other pegylated interferon products. P1101 was shown to have slightly longer half-life but maintain serum 2'5'-oligoadenylate synthetase (OAS) activity longer than the other pegylated interferon products.

15.12 **Formulation:** P1101 will be supplied in a pre-filled syringe containing 500 micrograms ropeginterferon alfa-2b, sodium chloride, sodium acetate, acetic acid, benzyl alcohol, polysorbate 80 and water for injection

15.13 **Storage:** Syringes are shipped in cooled containers. Syringes must be refrigerated at 2°C-8°C immediately upon receipt to ensure optimal retention of physical and biochemical integrity and should remain refrigerated until just prior to use. Temperature logs must be maintained (in accordance with local pharmacy practice) to ensure proper storage conditions. Do not use medication beyond the

expiration date stamped on the vial. If a temperature deviation from the allowed 2°C-8°C is found either during shipment or storage then please contact the Sponsor to determine if the drug is still available for use. Refrigerated syringes at 2°C-8°C must have the following conditions adhered to: Do not freeze. Do not shake. Keep syringe in outer carton; protect from light.

Study medication labels will contain the following information: site number, subject number, visit number, product description, dosage strength, dosing instruction, expiry date, lot number, storage conditions, and caution statements.

15.14 Administration: P1101 should be given by subcutaneous injections in the abdomen around but not within two inches of the navel. If the abdomen appears inappropriate according to the investigator's judgment, then study drug can be injected subcutaneously to the thigh.

15.15 Pharmacokinetic information: Mean P1101 serum concentration time curves were comparable across treatment groups and reached a peak at approximately 3 to 5 days after dosing and then declined gradually, with elimination half-lives of 60 to 118 hours. Single dose pharmacokinetic parameters (Cmax, AUC and AUC0-t) for P1101 increased with dose. The results of the power model analysis of dose proportionality for P1101 suggested more than proportional kinetics with increasing dose, as the slopes of the power model ranged from 1.19 to 1.36. The lack of dose proportionality for P1101 in this study may be attributed partly due to the high intersubject pharmacokinetic variability, and the small number of subjects.

15.16 Potential Drug Interactions: No information available.

15.17 Known potential toxicities: Adverse events reported most frequently (>10% of subjects) in either treatment in the *single dose* study include injection site erythema, headache, myalgia, decreased neutrophil count, back pain, increased body temperature, decreased white blood cell count, arthralgia, chills, fatigue, eye pain, feeling cold, nausea, increased alanine aminotransferase, somnolence, upper respiratory tract infection, feeling hot, decreased appetite, and pyrexia.

Adverse events reported in the *repeated dose* study have so far been mild to moderate. These include anemia, dizziness, dry mouth, dry skin, dyspnea, ear pain, epigastralgia, epistaxis, fatigue, fidget, flank pain, headache, myalgia, pruritus, respiratory distress, skin allergy, skin erythema, somnolence, sore throat, UTI, WBC decrease.

Investigators should also be informed of published data on marketed pegylated interferon. Subjects receiving *repeated doses* of interferon α -2b, have reported adverse events that include influenza-like symptoms, fever, headache, fatigue, rigors, musculoskeletal pain, arthralgia, back pain, injection site disorders (bruising, itching, and irritation), dry mouth, nausea/vomiting, diarrhea, abdominal pain, anorexia, weight, dizziness, impaired concentration, impaired memory, depression, anxiety/emotional lability/irritability, insomnia, alopecia, pruritus, dermatitis, rash, increased sweating, dyspnea, cough, and hypothyroidism. Common laboratory adverse events include neutropenia,

thrombocytopenia, increases in triglycerides and total cholesterol, abnormalities indicative of altered thyroid and liver function. Ten to fifteen percent of patients develop antibodies to interferon.

Serious adverse events that have been reported with this class of drugs include suicide attempt, suicidal ideation, severe depression, relapse of drug addiction/overdose, nerve palsy (facial, oculomotor), cardiomyopathy, myocardial infarction, retinal ischemia, retinal vein thrombosis, transient ischemic attack, supraventricular arrhythmias, loss of consciousness, neutropenia, infection (pneumonia, abscess), autoimmune thrombocytopenia, hyperthyroidism, rheumatoid arthritis, interstitial nephritis, lupus-like syndrome, aggravated psoriasis and urticaria.

15.18 Drug procurement: Drug is supplied by PharmaEssentia and provided free of charge to study subjects.

15.19 Nursing Guidelines:

15.191 Patients may experience injection site reactions including pain, erythema.

15.192 Monitor LFT's, report increases to the study team.

15.193 Monitor CBC w/diff. Leukopenia and neutropenia have been seen with agent.

15.194 Patients may experience fever. Treat symptomatically and monitor for effectiveness.

15.195 Arthralgias, and back pain were common. Treat symptomatically and monitor for effectiveness.

15.196 Given the similarity between this agent and pegylated IFN, patients may experience similar reactions and side effects. Carefully review those with patients based on the published data for pegylated IFN. Additionally this information is found in section 15.17 of the protocol.

16.0 Statistical Considerations and Methodology

16.1 Overview: This protocol will assess the efficacy of P1101 in patients with myelofibrosis using a two-stage phase II study design. Cohort 2 will be formally analyzed for safety and efficacy as described by the decision rules below. Cohort 1 analysis will be descriptive only; no formal efficacy decision rules will be applied. Recruitment occurs separately for cohort 1 and cohort 2. **We currently plan to enroll and complete Stage 1. The protocol will be amended to expand to Stage 2.**

16.11 Primary Endpoint (Cohort 1 & 2): The primary endpoint of this trial is best overall response. An evaluable patient will be classified as a treatment success for the primary endpoint if the patient's best overall response is CR, PR or CI (Clinical Improvement) as determined by International Working Group Criteria [detailed in Section 11.0] over all cycles of study treatment. All patients meeting the eligibility

criteria who have signed a consent form, have begun treatment, and have not experienced a major treatment violation within the first cycle of treatment will be evaluable for response. Any evaluable patient not meeting the definition for treatment success will be deemed as having a treatment failure. The primary endpoint will be formally tested based on the decision rules below for cohort 2. For cohort 1, the primary endpoint will be summarized for descriptive purposes only.

16.2 Statistical Design:

16.21 Decision Rule(Cohort 2 only) : The largest success proportion where the proposed treatment regimen would be considered ineffective in this population is 10%, and the smallest success proportion that would warrant subsequent studies with the proposed regimen in this patient population is 30%. The following two-stage Fleming design (1982) uses 12 or 35 patients to test the null hypothesis that the true success proportion in a given patient population is at most 10%.

16.211 STAGE 1(Cohort 2 only): Enter 12 patients into the study. If 0 successes are observed in the first 12 evaluable patients, we will consider this regimen ineffective in this patient population and terminate this study. If 4 or more successes are observed in the first 12 evaluable patients, we may recommend further testing of this regimen in subsequent studies in this population (a decision to complete the planned accrual specified by the design will be based on availability of budget, assuming no safety concerns). Otherwise, if the number of successes is 1, 2, or 3, we will consider a protocol amendment to expand to Stage 2. In cohort 2, after the first 3 patients are enrolled a recruitment pause will occur as a safety precaution measure. Safety/toxicity data will be analyzed in these 3 patients and a decision to continue the study will be made by the Principal Investigator, statistician and study team. .

16.212 STAGE 2(Cohort 2 only): Enter an additional 23 patients into the study. If 6 or fewer successes are observed in the first 35 evaluable patients, we will consider this regimen ineffective in this patient population. If 7 or more successes are observed in the first 35 evaluable patients, we may recommend further testing of this regimen in subsequent studies in this population.

16.213 Over Accrual: If more than the target number of patients are accrued, the additional patients will not be used to evaluate the stopping rule or used in any decision making process. Analyses involving over accrued patients is discussed in Section 16.34.

16.22 Sample Size: The two-stage study design to be utilized is fully described in Section 16.21. A minimum of 12 and a maximum of 35 evaluable patients will be accrued onto this phase II (Cohort 2 only) study unless undue toxicity is encountered. **We are currently planning to enroll to Stage 1 only.** We anticipate accruing an additional 1 patient to Stage 1 to account for ineligibility, cancellation, major treatment violation, or other reasons. Maximum projected accrual to Stage 1 is therefore **13 patients for cohort 2**. Anticipated enrollment in cohort 1 is expected to be low, therefore a maximum of 6 patients will be

enrolled in cohort 1. Cohort 1 will be analyzed for descriptive purposes only, Total sample size is a maximum of 19 patients in both cohorts for Stage 1.

16.23 Accrual Time and Study Duration: The anticipated accrual rate is approximately 1 patient per month. Therefore, the accrual period for Stage 1 of this phase II study is expected to be 19 months. The Stage 1 analysis can begin approximately 25 months after the trial begins, i.e., as soon as the last patient has been followed for 6 months.

16.24 Power and Significance Level (Cohort 2 only): Assuming that the number of successes is binomially distributed, the significance level is $>/=10\%$ and the probability of declaring that this regimen warrants further studies (i.e., statistical power) under various success proportions and the probability of stopping accrual after the first stage can be tabulated as a function of the true success proportion as shown in the following table. These computations assume that the study is carried out in its entirety (i.e., accrual continues to Stage 2 if indicated by the responses observed in Stage 1).

If the true success proportion is . . .	0.10	0.15	0.20	0.25	0.30	0.35
then the probability of declaring that the regimen warrants further studies is . . .	0.07	0.28	0.58	0.81	0.93	0.98
and the probability of stopping (and rejecting H_a) at stage 1 is . . .	0.28	0.14	0.07	0.03	0.01	<0.01
and the probability of stopping at stage 1 is . . .	0.31	0.23	0.27	0.38	0.52	0.66

16.25 Other Considerations: Adverse events, quality/duration of response, and patterns of treatment failure observed in this study, as well as scientific discoveries or changes in standard care will be taken into account in any decision to terminate the study.

16.3 Analysis Plan: The analysis for this trial will commence at planned time points (see Section 16.2) and at the time the patients have become evaluable for the primary endpoint. Such a decision will be made by the Statistician and Study Chair, in accord with CCS Standard Operating Procedures, availability of data for secondary endpoints (e.g., laboratory correlates), and the level of data maturity. It is anticipated that the earliest date in which the results will be made available via manuscript, abstract, or presentation format is approximately 19 months after the trial begins, i.e., as soon as the last patient has been followed for 6 months.

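### Section 16.24 gives the significance level as 10% or more, but its own table shows 0.07 at the null rate and the stated rule gives exactly 0.067

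*Combined protocol and SAP*

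**What the plan says.** Section 16.21 sets the null value: "The largest success proportion where the proposed treatment regimen would be considered ineffective in this population is 10" per cent. The rate that would justify further study is 30%. The design is a two-stage Fleming design with 12 or 35 patients, used to "test the null hypothesis that the true success proportion in a given patient population is at most 10" per cent.

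Sections 16.211 and 16.212 give the rule:

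- 0 successes in 12: the regimen is considered ineffective and the study stops.
- Positive at Stage 1: "If 4 or more successes are observed in the first 12 evaluable patients".
- 1, 2 or 3 successes in 12: expansion to Stage 2, with 23 more patients, is considered.
- Positive at Stage 2: "If 7 or more successes are observed in the first 35 evaluable patients".

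Section 16.24 then says "the significance level is $>/=10\%$ and the probability of declaring that this regimen warrants further studies" are as tabulated. The first result row, headed "then the probability of declaring that the regimen warrants further studies is", reads 0.07, 0.28, 0.58, 0.81, 0.93 and 0.98 at true success proportions of 0.10, 0.15, 0.20, 0.25, 0.30 and 0.35. The section adds the condition "These computations assume that the study is carried out in its entirety", meaning that Stage 2 is run when Stage 1 calls for it.

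**The concern.** The significance level of this one-sided test is the largest probability of a positive declaration while the null hypothesis is true. That probability rises with the true success proportion, so its maximum is at 0.10, and the table's entry there is 0.07. The sentence above the table puts the level at 10% or more. Both cannot be right.

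If the table were wrong, the cut-offs or the power figures might be wrong too, and the design would need rework. If the sentence is wrong, the protocol misdescribes the false-positive risk of its only formal efficacy test. It would then give a floor with no ceiling where a ceiling is needed, and that wording could be carried into a report or into the amendment that would open Stage 2. The check below decides which it is.

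**Working it through.** **Inputs.** Null rate 0.10 (16.21). Stage 1: n = 12, stop at 0, positive at 4 or more, continue on 1 to 3 (16.211). Stage 2: 23 further patients, positive at 7 or more of 35 in total (16.212). Successes are binomial (16.24).

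**Formula.** With X1 ~ Bin(12, p) and X2 ~ Bin(23, p):

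P(positive) = P(X1 ≥ 4) + Σ (k = 1 to 3) P(X1 = k) × P(X2 ≥ 7 − k)

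**At p = 0.10:**

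| Path | P(X1) | P(X2 ≥ 7 − k) | Product |
|---|---|---|---|
| X1 ≥ 4 | 0.0256 | – | 0.0256 |
| X1 = 1 | 0.3766 | 0.0226 | 0.0085 |
| X1 = 2 | 0.2301 | 0.0731 | 0.0168 |
| X1 = 3 | 0.0852 | 0.1927 | 0.0164 |

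Stage 1 contributes 0.0256. Stage 2 contributes 0.0418 (the rounded products sum to 0.0417). The total is 0.0674, which rounds to the printed 0.07.

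**The rest of the table.** The second row is P(X1 = 0). The third is P(X1 = 0) + P(X1 ≥ 4).

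| True p | Positive: exact (printed) | Stop for futility: exact (printed) | Any Stage 1 stop: exact (printed) |
|---|---|---|---|
| 0.10 | 0.0674 (0.07) | 0.2824 (0.28) | 0.3081 (0.31) |
| 0.15 | 0.2820 (0.28) | 0.1422 (0.14) | 0.2344 (0.23) |
| 0.20 | 0.5761 (0.58) | 0.0687 (0.07) | 0.2742 (0.27) |
| 0.25 | 0.8078 (0.81) | 0.0317 (0.03) | 0.3829 (0.38) |
| 0.30 | 0.9314 (0.93) | 0.0138 (0.01) | 0.5213 (0.52) |
| 0.35 | 0.9800 (0.98) | 0.0057 (<0.01) | 0.6590 (0.66) |

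All 18 cells match, so the rule and the table agree and only the sentence stands apart.

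**Does the level reach 10% anywhere under the null?** No. P(positive) is 0.003 at p = 0.05, 0.027 at 0.08, 0.044 at 0.09 and 0.067 at 0.10. It reaches 0.10 only at p = 0.111, outside the null region.

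**Would a neighbouring rule explain the sentence?** At p = 0.10, changing one cut-off at a time:

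| Rule | Level |
|---|---|
| As written (4/12, 7/35) | 0.067 |
| Final cut-off 6/35 | 0.132 |
| Final cut-off 8/35 | 0.039 |
| Stage 1 cut-off 3/12 | 0.136 |
| Stage 1 cut-off 5/12 | 0.055 |

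The two looser rules exceed 10%, but neither is written and neither gives the printed 0.07. With the other cut-off held fixed, 4/12 and 7/35 are each the smallest value that keeps the level at or below 10%. That fits a design built to an upper limit of 10%.

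**Other ways the trial could run.** If it ends at Stage 1 and only 4 or more of 12 counts as positive, the level is 0.026. If accrual is completed after 4 or more of 12, and the 7/35 rule is then assumed to decide, it is 0.054. Both are below 10%.

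**The case against.** The strongest reply is that this is one reversed sign with no operational effect. No boundary, sample size, analysis or power figure depends on the sentence. The correct value stands in the table just below it, so a careful reader is not misled for long. The error also overstates the false-positive risk and hides no inflation. All of that is true and keeps the point small. It does not make the sentence correct, and this is the only sentence that puts the level of the formal test into words.

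A second reply is that the symbol may have been misread from the PDF. That cannot be excluded from the text alone, and a look at the source page would settle it. It is unlikely: combined inequality signs in the eligibility section were read as proper mathematical symbols, whereas this one appears as typed characters.

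A third is that the documents state no target level elsewhere, so reading the intended wording as at most 10% is an inference. That is fair. The exact figure is not an inference, however, and giving it removes the need to guess.

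Finally, Section 16.22 says "We are currently planning to enroll to Stage 1 only", so the two-stage level may never apply. Section 16.24 already discloses that its figures assume Stage 2 is run when indicated, and the Stage 1 level alone is lower still.

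**Conclusion.** The concern holds. The sentence in Section 16.24 states a level of 10% or more, while the table and the stated rule give 0.07 (exact 0.0674) at the null rate of 0.10. The rule, sample sizes and all table entries are correct. The error is confined to the inequality and is most likely a reversed sign.

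The result assumes binomial counts, exactly 12 and 35 evaluable patients, and continuation to Stage 2 after 1 to 3 successes, as Section 16.24 itself assumes. The consequence is limited to a wrong statement of a design property. It is still worth correcting because it describes the trial's only formal efficacy test.

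**What to change.** In Section 16.24, replace the stated level with: at most 10% (exact 0.067 for the completed two-stage design). If the sponsor prefers not to name a nominal limit, giving the exact 0.067 alone is enough. Check the sign against the source page when making the change.

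The cost is one inequality sign and a short parenthesis. No patients are added, and no cut-off, table entry or sample size changes. The correction can go into the next amendment, for example the one needed to open Stage 2.

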16.31 Primary Endpoint (Both Cohorts)

16.311 Definition: The primary endpoint of this trial is the best overall response rate where a response is defined in Section 16.11.

16.312 Estimation: The proportion of successes will be estimated by the number of successes divided by the total number of evaluable patients. Confidence intervals for the true success proportion will be calculated according to the approach of Duffy and Santner (1987).

16.313 Over Accrual: If more than the target number of patients are accrued, the additional patients will not be used to evaluate the stopping rule or used in any decision making processes; however, they will be included in final point estimates and confidence intervals as though they were accrued in the final stage.

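### If cohort 2 runs as the two-stage rule tabulated in 16.24, the raw response proportion in 16.312 is biased (about -1.4 points at a true 10%, +3.3 at 30%); a stage-adjusted estimate should be reported beside it

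*Combined protocol and SAP*

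**What the plan says.** - **Estimator (16.312, both cohorts):** "The proportion of successes will be estimated by the number of successes divided by the total number of evaluable patients". No stage-adjusted estimate is given and bias is not mentioned. The interval method is named (Duffy and Santner, 1987) but not described.
- **Design (16.21, cohort 2):** "The following two-stage Fleming design (1982) uses 12 or 35 patients to test the null hypothesis" that the success rate is at most 10%; 30% is the smallest rate regarded as worth pursuing.
- **Lower stop (16.211):** "If 0 successes are observed in the first 12 evaluable patients, we will consider this regimen ineffective in this patient population and terminate this study".
- **Upper boundary (16.211):** "If 4 or more successes are observed in the first 12 evaluable patients, we may recommend further testing of this regimen". A parenthesis then leaves completion of the planned accrual to budget, provided there is no safety concern.
- **Between the boundaries (16.211, 16.212):** after 1, 2 or 3 successes the team will consider an amendment that adds 23 patients. The final criterion is 7 or more of 35.
- **Status of Stage 2:** 16.22 plans enrolment to Stage 1 only for now. 16.1 says "The protocol will be amended to expand to Stage 2". The 16.24 table assumes that both stages are run where indicated.

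**The concern.** When the sample size depends on the result, successes divided by patients is generally not unbiased. Under the rule tabulated in 16.24, a high Stage 1 result is reported as it stands on 12 patients, while a result of 1-3 is averaged with 23 more. High early results keep their full weight and middling ones are pulled towards the true rate. A stop at 0/12 works in the opposite direction.

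The response rate is the main reported result and a natural planning figure for a later study. Under the tabulated rule, the raw figure is on average too favourable around the 30% that 16.21 treats as worthwhile, and too low around the 10% null.

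**Working it through.** **Inputs.** First-stage size 12, second-stage size 23, lower stop at 0, upper boundary at 4, final criterion 7 of 35 (16.21, 16.211, 16.212); true rates as in the 16.24 table. Write b(x) for the binomial probability of x successes in 12 at true rate p.

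**Step 1: reproduce 16.24.** Stop at 0 or at 4 or more, continue at 1-3, declare success at 4 or more of 12 or at 7 or more of 35.

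| True rate | 0.10 | 0.15 | 0.20 | 0.25 | 0.30 | 0.35 |
|---|---|---|---|---|---|---|
| Declare success, recomputed | 0.067 | 0.282 | 0.576 | 0.808 | 0.931 | 0.980 |
| Declare success, 16.24 | 0.07 | 0.28 | 0.58 | 0.81 | 0.93 | 0.98 |
| Stop at Stage 1, recomputed | 0.308 | 0.234 | 0.274 | 0.383 | 0.521 | 0.659 |
| Stop at Stage 1, 16.24 | 0.31 | 0.23 | 0.27 | 0.38 | 0.52 | 0.66 |

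The futility-stop row also matches. At 30%, 0.521 stop at Stage 1, of which 0.014 is the lower stop and 0.507 the upper, so 16.24 does count the upper boundary as a stop.

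**Step 2: bias under the tabulated rule.** A stop reports x/12. Continuation reports (x + 23p)/35 on average. If every trial went to 35 the bias would be zero, so the bias is the sum over stopping outcomes of the difference between these two:

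bias = (23/35) × Σ over x in {0, 4, ..., 12} of b(x)(x/12 − p)

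- At p = 0.30: the lower stop gives 0.0138 × (−0.30) = −0.0041. The upper stop gives 0.2062 − 0.30 × 0.5075 = +0.0539, where 0.2062 is the sum of (x/12)b(x) for x of 4 or more. Bias = 0.657 × 0.0498 = **+0.033**.
- At p = 0.10: the lower stop gives 0.2824 × (−0.10) = −0.0282. The upper stop gives 0.0090 − 0.10 × 0.0256 = +0.0064. Bias = 0.657 × (−0.0218) = **−0.014**.
- Likewise −0.001 at 0.15, +0.014 at 0.20, +0.027 at 0.25 and +0.032 at 0.35. The sign changes near 15%.

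The standard deviation of the raw proportion is 0.076 at 10%, 0.110 at 20% and 0.110 at 30%.

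**Step 3: bias under the other paths that the text allows.**

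- Accrual always ends at 12: X/12 has bias 0 at every p.
- Accrual continues to 35 after 4 or more of 12: only the lower stop remains, so bias = −(23/35) × p × (1 − p)^12. At 0.10 this is −0.657 × 0.10 × 0.2824 = −0.019. At 0.30 it is −0.657 × 0.30 × 0.0138 = −0.003.

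**Step 4: a stage-adjusted estimate.** Take the p whose expected raw proportion, under the rule followed, equals the observed proportion. Under the tabulated rule the expected raw proportion at p = 0.30 is 0.333, so an observed 4/12 maps to 30.1%. Likewise 7/35 (20.0%) maps to 18.9% and 10/35 (28.6%) to 25.8%.

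| True rate | 0.05 | 0.10 | 0.20 | 0.25 | 0.30 | 0.35 | 0.40 |
|---|---|---|---|---|---|---|---|
| Bias, raw (points) | −1.7 | −1.4 | +1.4 | +2.7 | +3.3 | +3.2 | +2.7 |
| Bias, adjusted (points) | −1.1 | −0.9 | +0.2 | +0.7 | +0.9 | +0.8 | +0.4 |
| Root mean squared error, raw | 0.047 | 0.077 | 0.111 | 0.115 | 0.115 | 0.115 | 0.117 |
| Root mean squared error, adjusted | 0.050 | 0.073 | 0.098 | 0.105 | 0.109 | 0.115 | 0.122 |

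**Step 5: the adjustment must match the rule followed.** If the tabulated-rule adjustment were applied when accrual always ended at 12, bias at 30% would go from 0 to −1.8 points. If accrual continued past 4/12, it would go from −0.3 to −2.7.

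**The case against.** The strongest reply is that the plan now authorises Stage 1 only. On 12 patients whatever the result, X/12 is exactly unbiased, and an amendment opening Stage 2 would be a natural place for a new estimator. That stands, and it makes the point conditional. It does not remove it, because 16.1 foresees the expansion and 16.24 describes the full design. The estimator is also best fixed before the Stage 1 count is known.

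Second, the +3.3 points come from the upper stop, which 16.211 leaves open. This also stands: a reader might infer that the raw rate is simply 3.3 points too high at 30%, but the documents support that only for the rule as tabulated.

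Third, the adjusted value depends on the estimator chosen. The exactly unbiased estimator leaves 4/12 at 33.3% and gives 20.5% for 10/35, against 30.1% and 25.8% here. So 30.1% is not the uniquely correct reading of 4/12. This is why one estimator must be named in advance and the raw figure kept beside it.

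Fourth, the bias is small against sampling error, and the adjusted estimate has slightly larger root mean squared error at 5% and 40%. Both are true.

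A reader might also infer that 16.312 is inconsistent because its interval allows for the stages while its estimate does not. The documents only name the interval method. Section 16.313 counts over-accrued patients in the final stage for the estimate and the interval, which is at most a hint. The bias result does not need this inference.

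**Conclusion.** The point holds in conditional form. If both Stage 1 stops are taken and Stage 2 follows 1-3 successes, the raw proportion understates the rate near 10% and overstates it from about 15% upwards, by at most about 3.3 points at the tabulated rates. Where accrual continues after 4 or more of 12, a smaller downward bias remains; where accrual always ends at 12, there is none. The results assume binomial counts, exactly 12 or 35 evaluable patients, and adherence to the stated path.

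It would be wrong to infer that a decision is affected: 16.211 and 16.212 decide on counts. What is affected is the reported size of the response rate, moderately. This is a cheap improvement to the primary estimate, not a flaw in the design.

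**What to change.** Before the Stage 1 data are seen:

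1. In 16.211, state whether the stop at 4 or more of 12 is binding, and whether Stage 2 will follow 1-3 successes.
2. In 16.312, for cohort 2 under the two-stage rule, keep the raw proportion and report beside it one pre-specified stage-adjusted estimate: the p whose expected raw proportion under the rule actually followed equals the observed one.
3. State that if accrual ends at 12 whatever the result, X/12 is reported alone. Cohort 1 keeps the raw proportion.

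The cost is a few sentences and a few lines of code. The downside is a second reported figure that, under the tabulated rule, is slightly less favourable for results above about 15% and whose value depends on the chosen estimator, so the text should name that estimator.
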